6.3. Handling of Missing Data

Subjects who discontinue the study prior to or after the initiation of the study drug will not be replaced and available data of these subjects until the point of discontinuation will be summarized. The missing baseline assessment will not be imputed.

For categorical variables with missing values, a category documenting the frequency of missing values will be displayed in the summary tables.

Subjects who discontinue early will be requested to complete all EOS procedures and assessments at an early termination visit.

There will be no imputation of missing values for safety data, however missing relationship between AE and study drug will be considered as related to study drug following worst case principle. Missing severity of an AE will be summarized as a severe AE.

Immunogenicity samples with a positive titer value will undergo a log transformation for analyses. Samples with titer level less than 1 will be assigned or imputed as a log transformed titer of zero (0) for analyses.

PR-CIS total score when scores are missing

If scores on at least two of the 6 items are missing, then PR-CIS total score will be calibrated to 6 and computed as:

- Total PR-CIS Score = (Sum of the Scores ÷ Number of question answered) x 6

If scores on three or more of the six items are missing, then the PR-CIS total score will be set to missing.

PR-CIS abbreviated total score when scores are missing

If scores on at least of the 5 items are missing, the PR-CIS abbreviated total score will be computed as:

- Abbreviated total PR-CIS Score = (Sum of the Scores ÷ Number of question answered) x 5

If scores on three or more of the five items are missing, then the PR-CIS abbreviated total score will be set to missing.

Composite response when PR-PCSS and/or CR-PCSS component missing

If the classification is missing for 1 or both components (ie, the PR-PCSS component or the CR-PCSS component), then the composite responder classification is missing for that visit.

6.3.1. Imputation of Partial Dates

6.3.1.1. Adverse Event Status for Completely Unknown AE Start Date

The following rules will apply in cases where start date of an AE is completely unknown before retreatment:

- If the AE onset date is unknown and the end date is on or after Day 71/EOS visit date of double-blind studies but before start of open-label period for the subjects who moved to open-label period OR end date is on or after Day 71/EOS visit date of double-blind studies for subjects who didn't enter open-label period, then the AE will be associated with 'Day 71/EOS Phase 3 – until start of open-label period.'
- If the AE onset date is unknown and the end date is on or after start of Open-label period but before M12 assessment date, then the AE will be associated with 'Start of Open-label period – Day 360 (M12)' period.
- If the AE onset date is unknown and the end date is on or after M12 visit date but before M18 assessment date, then the AE will be associated with 'Day 360 (M12) – Day 540 (M18)' period.
- If the AE onset date is unknown and the end date is on or after M18 visit date but before M24 assessment date, then the AE will be associated with 'Day 540 (M18) – Day 720 (M24)' period.
- If the AE onset date is unknown and the end date is on or after M24 visit date but before M36 assessment date, then the AE will be associated with 'Day 720 (M24) – Day 1080 (M36)' period.

The following rules will apply in cases where start date of an AE is completely unknown after retreatment:

- If the AE onset date is unknown and the end date is on or after Day 1 visit date but before Day 22 visit date, then the AE will be associated with Treatment Session 1.
- If the AE onset date is unknown and the end date is on or after Day 22 visit date but before Day 43 visit date, then the AE will be associated with Treatment Session 2.
- If the AE onset date is unknown and the end date is on or after Day 43 visit date but before Day 71 visit date, then the AE will be associated with Treatment Session 3.
- If the AE onset date is unknown and the end date is on or after Day 71 or ongoing, then the AE will be associated with the observation assessment and will be imputed as:
 - If the AE onset date is unknown and the end date is on or after Day 71 visit date of retreatment session but before M12 assessment date, then the AE will be associated with 'Day 71 – Day 360 (M12)' period.
 - Remaining imputation of missing AE start date after retreatment is similar to the imputation outlined for 'before retreatment'
- If the AE onset date is partly present, month/year will be used to identify the treatment session and time period association.

6.3.1.2. Concomitant Status of Medication for Completely Unknown Start Date

The following rules will apply in cases where start date of concomitant medication is completely unknown:

- If the medication onset date is unknown and the end date is after the informed consent date or ongoing, then the medication will be considered as concomitant.
- If the medication onset date is unknown and the end date is before the informed consent, then the medication will not be considered as concomitant.
- If both the start and end dates are unknown (or medication is ongoing), then the medication will be considered as concomitant, following the worst-case principle.

If the medication onset date is partly present and month/year is prior to the informed consent, then the medication will not be considered as concomitant.

6.4. Interim Analyses

As this is an observational study hence no formal interim analyses are planned. However, for Biologics License Application (BLA) submission an analysis for safety, reduction of response and complete loss of response analysis, and other cellulite assessments will be performed at Day 180 data cutoff and data cutoff for 4-month safety update after BLA-submission.

6.5. Treatment Groups and Summary Groups

One (1) retreatment course of CCH is comprised of three treatment sessions will be administered in up to 2 qualifying buttocks in this study.

For the Day-180 Observational Population and Prior to Day 180 Population, the summary tables will be presented by treatment arm (ie, CCH 1.68 mg, Placebo, and Overall) in double-blind studies (EN3835-302/303). For the Open Label Observation Population, the summary tables will be presented by Subject Category (ie, Category I, II, III, and Overall). The summary tables will be presented by Subject Category (ie, Category I, II, and Overall) in OLR Population, OLN Population and TRR Population Before and After Retreatment.

7. STATISTICAL ANALYSES

7.1. Subject Disposition

The disposition summary table will include the disposition details of all the rollover subjects from the double-blind studies to this open-label extension study. The disposition data will be summarized by number and percentage of subjects for all the subjects in the 180 Day Observational Period and Open-label Period of the study.

For 180 Day Observational Period and Prior to Day 180 Population, the subject disposition summary table will include following information by treatment arm (CCH 1.68 mg, Placebo, and Overall) in the double-blind studies EN3835-302/303:

- Subjects screened
- Screen failure

- Subjects enrolled
- Completed up to Day 180 period
- Completed Day 180 and informed consent form signed for the 3 Year Observational Period
- Completed Day 180 and then Discontinued prior to Open-label Period
- Discontinued in Day 180 period
 - Reason of discontinuation (including subjects who received placebo in the double-blind studies)
- Subject Populations
 - Day 180 Observational Population
 - TRR Population Before Retreatment

For Open-label Period, the subject disposition summary table will include following information subject category (Category I, Category II, Category III, and Overall)

- Subjects entered Open-label Period
- Subject Populations
 - Open Label Observation Population
 - TRR Population Before Retreatment
 - OLR Population
 - OLNLR Population
 - TRR Population After Retreatment
- Completed the study
- Discontinued the study
 - Reason of discontinuation
- Discontinued during the following time period
 - Start of Open-label Period– Day 360 (M12)
 - Day 360 (M12) – Day 540 (M18)
 - Day 540 (M18) – Day 720 (M24)
 - Day 720 (M24) – Day 1080 (M36)

In addition, time in the study will be summarized descriptively, this will include all Category I, II, and III subjects (see [Table 17](#) for computation of time in study).

A listing of disposition from 180 Day Observational Period and disposition from Open-Label Period who entered the Open-Label Period will be provided separately. In addition, the discontinued subjects from the study and screen failures from study will also be listed.

A listing of subject excluded from different analysis population will be provided.

7.2. Protocol Deviations

A listing of all protocol deviations will be presented for All Subjects.

7.3. Demographics and Baseline Characteristics

Demographics characteristics will be summarized for the Day-180 Observational Population, Prior to Day 180 Population, Open-label Observation Population, TRR Population Before Retreatment, OLR Population, OLNLR Population and TRR Population After Retreatment. For Day-180 Observational Population, the Demographics characteristics will be summarized by treatment arm (ie, CCH 1.68 mg, Placebo, and Overall) in the double-blinded studies (EN3835-302/303), for Open Label Observation Population the demographics characteristics will be summarized by Subject Category (ie, Category I, II, III, and Overall), and for TRR Population Before and After Retreatment and OLR Population the demographics characteristics will be summarized by Subject Category (ie, Category I, II, and Overall).

Age, height (at screening), body weight (at screening) and body mass index (BMI) in kg/m² will be summarized as continuous variables using descriptive statistics.

Age category (<25, 25-34, 35-44, and ≥45 years of age), gender, race and ethnicity will be summarized as categorical variables using frequency counts and percentages.

All demographic characteristics will be presented in listing for All Subjects.

7.4. Medical History

Any newly discovered medical history (ie, events/procedures) that occurred prior to enrollment in study EN3835-302/303 and which was not reported earlier will be listed for all subjects and for Prior to Day 180 Observational Population will be presented separately.

7.5. Prior and Concomitant Medications/Procedures

Prior and concomitant medications will be summarized using frequency counts and percentages by active ingredient within each ATC, with ATC and active ingredients ordered alphabetically. Multiple use of the same medication by a subject will be counted only once.

Prior and concomitant medications will be summarized for the Day-180 Observational Population and Prior to Day 180 Population by treatment arm (ie, CCH 1.68 mg, Placebo, and Overall). Concomitant medications will be summarized for the Open-label Observation Population by Subject Category (ie, Category I, II, III, and Overall), and OLR Population by Subject Category (ie, Category I, II, and Overall).

The subject listings of prior and concomitant medications/procedures will be presented for All Subjects and for Prior to Day 180 Observational Population will be presented separately.

The separate listings of prior and concomitant medications/procedures and EFP/Cellulite will also be provided for All Subjects as well as for Prior to Day 180 Observational Population.

7.6. Efficacy Analyses

Efficacy parameters in 180 Day Observational Period will be summarized by subject category at treatment area (ie, left and/or right buttock separately) by treatment arm (ie, CCH 1.68 mg, Placebo, and Overall) for subjects in Day 180 Observational Population and Prior to Day 180 Population.

Efficacy parameters in Open Label Period will be summarized by subject category at treatment area (ie, left and/or right buttock separately) for subjects in the TRR Population Before Retreatment and TRR Population after Retreatment separately.

7.6.1. Changes in the PR-PCSS and CR-PCSS from Baseline

For Day 180 visit, the observed and change from Day 1 and Day 71/EOS of double blind study for PR-PCSS and CR-PCSS scores will be analyzed separately during using Day-180 Observational Population,

The PR-PCSS and CR-PCSS ratings and change from Day 1 and Day 71/EOS severity ratings (ie, Day 71/EOS of double-blind study) in Open-label Period will be summarized by treatment area (ie, separately for left and right buttock), assessment visits (baseline and all the post baseline observations) and subject category using counts and percentages at each severity rating and with mean and SD, for subjects in TRR Population Before Retreatment and OLNLR Population.

For during and after retreatment period, the same analysis will be repeated using OLR Population.

7.6.2. Reduction of response using PR-PCSS and CR-PCSS Prior to Retreatment

The proportion of subjects or buttocks with reduction of response (refer to section 4.4.1) will be summarized using frequency counts and percentages using TRR Population Before Retreatment and OLNLR Population subject category (ie, Category I and II, and Overall) and treatment area (ie, left and/or buttock) at the following visits prior to retreatment: Day 180, Month 12, 18, 24, and 36 where reduction of response is assessed.

The proportions will be computed based upon number of subjects within each category and treatment area remains not-retreated prior to that visit.

The following efficacy end points for reduction of response will be summarized:

- Proportion of subjects with 2-level composite reduction
- Proportion of subjects with 1-level composite reduction
- Proportion of subjects with complete loss of response

The time to composite reduction of response (ie, by 1-level and 2-level separately) and time to complete loss of response (refer to section 4.4.1 for derivation) will be summarized descriptively using TRR Population Before Retreatment and OLNLR Population.

The listings of cellulite PR-PCSS and CR-PCSS severity ratings will be provided for All Subjects prior to retreatment.

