3.1.2. Category II

Subjects should have not received any collagenase treatments since the completion of double-blind study.

Subjects who showed an improvement in cellulite severity of at least two levels in at least one buttock in both the PR-PCSS and the CR-PCSS (ie, 2-level composite responder) in the double-blind study.

These subjects will be observed for time to reduction of response (defined in section 4.4.1) and safety approximately every 6 months for 2 years and will be observed annually for up to 3 years (Day 1080) from Day 71 of the double-blind study.

- Category II subjects must have at least 1-level composite response reduction (ie, reduction of response by at least 1-level in the PR-PCSS and CR-PCSS ratings) compared to Day 71 of the double-blind study (EN3835-302/303) AND no longer maintain 2-level composite response compared to baseline in the EN3835-302/303 study on either or both buttocks to be eligible for a retreatment course. If there is a composite worsening of cellulite severity, the confirmation of loss of response will be established during a follow-up visit ~2 weeks after the loss of response is detected at Day 180, if the loss of response is not confirmed then the subject will not be eligible for retreatment in this study.

One and only one retreatment course in up to 2 qualifying buttocks concurrently will be offered to eligible Category I and Category II subjects during this 3-year study. The subjects in Category I and/or eligible Category II subjects will receive a retreatment course consisting of 3 treatment sessions separated by 21 days (Day 1, 22, and 43). Each treatment session will consist of 12 injections (0.07 mg/0.3 mL per injection) of CCH for a dose of 0.84 mg and volume of 3.6 mL (identical to the treatment course administered in the double-blind study), in each qualifying buttock (see

Table 5) in up to two buttocks treated concurrently.

After initiation of retreatment, the safety and cellulite severity will be assessed on Days 22, 43, and 71. The Category I and Category II subjects who received retreatment will have safety assessment completed during the observational visits at Months 12, 18, 24, and 36 from Day 71 of the double-blind study.

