The Category II subjects that have not shown at least 1-level composite reduction AND/OR have a buttock that has maintained at least a 2-level composite response (ie, have maintained a successful response), and/or Category I and/or Category II subjects who are eligible for a retreatment course but opted not to receive retreatment will have cellulite assessments at Months 12, 18, 24, and 36 from Day 71 of the double-blind study. If the subject's buttock(s) become eligible for retreatment based on the ratings during an observational visit and if they have not already received a course of retreatment in this study, then they will be offered one course of retreatment for the eligible buttock(s); one course of concurrent treatment for up to two eligible buttocks.

If a treatment period overlaps a scheduled observational visit, the observational visit will be skipped, and the subject will re-enter the observational schedule at the next interval visit. For example, if a subject initiated retreatment on Day 351 (which would then be Treatment Visit 1), the treatment period would proceed for approximately 71 days until Day 421 (Treatment Visit 4) and the Observational Visit at Day 360 would be skipped; the subject's next observational visit would be Day 540.

[figure not shown]

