 - ⁱ Up to 4 hours before injection; approximately 15 and 30 minutes after injection. Pulse and blood pressure to be taken after subject has been sitting for 5 minutes. Vital signs must be stable before the subject is discharged. Refer to section 14.9 of Protocol Amendment 3.
 - ^j Do not conduct if Screening B visit date is within 12 months of obtaining an ECG during the double-blind study (EN3835-302/303).
 - ^k Serum pregnancy test on Screening visit and Day 71/EOS visit; urine pregnancy test on Day 1, Day 22, and Day 43 visits and Unscheduled Visit.
 - ^l Assessment made via photographs (if treatment visit, use photographs taken before marking dimples and injection sites).
 - ^m Subject assessments should be completed independently and prior to investigator assessments at each visit. Includes bot buttocks regardless of treatment, each buttock should be assessed independently.
 - ⁿ At least one of the Category I subject’s buttocks must have scores/ratings of at least 2 in both the CR-PCSS and PR-PCSS to be eligible to receive treatment. Category II subjects must have at least a 1-level composite response reduction compared to Day 71 of the EN3835-302/303 study AND no longer maintain a 2-level composite response compared to baseline in the EN3835-302/303 study on either or both buttocks.
 - ^o Local adverse events associated with the injection site, including acute (eg, erythema, bruising, pain, nodules/mass, ulceration, blistering, pruritus, swelling, and/or induration) and/or chronic (eg, skin thickening, fibrosclerosis, peau d’orange changes) cutaneous adverse events, will be recorded and evaluated for seriousness and severity.
- ECG=Electrocardiogram; EFP=Edematous fibrosclerotic panniculopathy; EOS=End of study; Tx=Treatment.

The Schedule of Events beyond Day 180 for subjects in Category I and II who are eligible and opted to receive retreatment, for the subjects in Category II who are not eligible for retreatment, and Category I and II subjects who are eligible but opted not to have retreatment is provided in [Table 3](#).

Table 3: Schedule of Events: Category I/II Subjects – Observation Assessments

	OBS Visit 2 Day 360 (±30 d) (M12)	OBS Visit 3 Day 540 (±30 d) (M18)	OBS Visit 4 Day 720 (±30 d) (M24)	OBS Visit 5 Day 1080/EOS/Early Termination (±30 d) (M36)	Durability Confirmation Visit^b
Procedures^a					
Verification of informed consent	X				
Inclusion/exclusion	X				
Digital photography	X	X	X	X	X

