3.2.1.5. Retreatment Subjects (Post Unblinding of EN3835-302/303)

Subjects in Category I and Category II who opt for retreatment must meet the following additional inclusion criteria to be eligible for retreatment. These subjects must:

1. Voluntarily sign and date an informed consent agreement for retreatment.
2. Be willing to apply sunscreen to the buttocks before each exposure to the sun while participating in the retreatment portion of the study (ie, Treatment Visit 1 through Treatment Visit 4).
3. Be judged to be in good health, based upon the results of a physical examination, and laboratory profile at Screening.
4. Have a negative serum pregnancy test at Screening and a negative urine pregnancy test before injection of study drug and be using a stable and effective contraception method (eg, abstinence, intrauterine device (IUD), hormonal [estrogen/progestin] contraceptives, or double barrier method) for at least 1 menstrual cycle prior to study enrollment and for the duration of the study; or be menopausal defined as 12 months of amenorrhea in the absence of other biological or physiological causes, as determined by the Investigator; or post-menopausal for at least 1 year; or be surgically sterile.
5. Category II subjects must have at least a 1-level composite response reduction compared to Day 71 of the EN3835-302/303 study AND no longer maintain a 2-level composite response compared to baseline in the EN3835-302/303 study on either or both buttocks that is confirmed at a Confirmation Visit.

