Open Label Retreated (OLR) Population	The OLR Population includes all subjects in TRR population who are retreated in the open label period of this study.	The analyses of cellulite assessments after retreatment ie, improvement of response during retreatment phase (Day 1 to Day 71+5 days of retreatment), study drug exposure during retreatment, Safety assessments after retreatment will be based on this population.
Open Label Not Retreated (OLNR) Population	The Open Label Not Retreated Population includes all subjects in TRR Population who are NOT retreated in the open label period of study.	All analyses for change from baseline in Day 1, or Day 71, and responder analysis based on this population will be performed
Time to Reduction of Response (TRR) Population After Retreatment	The TRR Population After Retreatment includes all subjects in OLR Population who have at least 1 level or 2-level improvement in both CR-PCSS and PR-PCSS ratings at Day 71/End of Treatment Session in the open label retreatment period. Reduction of response will be evaluated separately for subjects who have at least a 1-level and 2 level improvement in both CR-PCSS and PR-PCSS ratings during the open label treatment period in each treated buttock. The reduction of response after retreatment will be analyzed using this population.	The reduction of response in open label retreatment period compared to the score at Day 71 of retreatment period will be based on this population.

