8. CHANGE FROM PROTOCOL

This SAP is prepared based on the study protocol, original version dated 31-Jan-2018, Amendment 1 dated 19-Apr-2018, Amendment 2 dated 01-Nov-2018, and Amendment 3 dated 14-Jan-2021.

The changes in SAP from what is proposed in protocol is explained in Table 18 below:

Table 18: Changes from Protocol

Text in Protocol	Change in SAP	Justification

Overall Safety Population: All safety analyses will be based on this population. In addition, the safety data will be summarized by treatment period for those retreated subjects with EN3835.
	
Overall Safety Population is renamed as “Open-label Observation Population”
	
Safety profile in this study will be analyzed in two different phases, prior to retreatment phase and after retreatment phase. Hence these populations are defined.
 
The data prior to retreatment will be summarized based on Open-label Observation Population, and data after retreatment will be summarized based on Open-label Retreated Population (Refer to section 5).

TRR Population: The TRR population is defined as all subjects who have at least a 1-level or 2-level improvement in both CR-PCSS and PR-PCSS ratings during the double-blind study for either/both treated buttocks. This population will include Category I and II subjects. TRR will be evaluated separately for subjects who had a 1-level and 2-level composite improvement in CR-PCSS and PR-PCSS during studies EN3835-302/303 in each buttock.
	
Instead of TRR Population, it is renamed as ‘TRR Population Before Retreatment’
	
Reduction of Response will be assessed separately for prior to retreatment and after retreatment. Hence these populations are defined.
 
TRR Population Before Retreatment will include the subjects who are not-retreated and until the point prior to retreatment for the subjects who are retreated (Refer to section 5).
 
TRR Population After retreatment will only include the subjects who are retreated in this study and have at least 1 level or 2 level improvement in both CR-PCSS and PR-PCSS ratings at Day 71/End of Treatment Session in the open label retreatment phase (Refer to section 5).

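### The Month 12 to 36 loss-of-response proportions exclude areas already retreated; because Category II areas are retreated only after losing response, these figures understate cumulative loss in that category

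*SAP*

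**What the plan says.** Section 7.6.2 summarizes three proportions before retreatment: 2-level composite reduction, 1-level composite reduction and complete loss. They are reported at Day 180 and Months 12, 18, 24 and 36, by category and buttock. The denominator is stated: "The proportions will be computed based upon number of subjects within each category and treatment area remains not-retreated prior to that visit". The main population is the TRR Population Before Retreatment. Table 18 in section 8 says that this population uses data "until the point prior to retreatment for the subjects who are retreated".

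The same section repeats the proportions and the time variables in the OLNR Population (spelled OLNLR there). Table 16 defines it: "The Open Label Not Retreated Population includes all subjects in TRR Population who are NOT retreated in the open label period of study".

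The rules for retreatment differ by category.

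- **Category II.** Section 3.1.2 says "Category II subjects must have at least 1-level composite response reduction" relative to double-blind Day 71, and the 2-level response must also have been lost. Section 3.2.1.5 requires this "on either or both buttocks that is confirmed at a Confirmation Visit". The offer recurs at later observational visits for subjects not yet retreated.
- **Category I.** Table 2, footnote n, says that at least one of the subject's "buttocks must have scores/ratings of at least 2 in both the CR-PCSS and PR-PCSS to be eligible to receive treatment". No loss is required.

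After retreatment the area moves to section 7.6.3, with a new reference point at Day 71 of the retreatment course (Table 17). No rule carries the earlier loss forward in 7.6.2.

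**The concern.** For Category II, retreatment works as a rescue: losing response is what makes an area eligible for it. A table restricted to areas not yet retreated therefore sheds losers selectively, and sheds more of them the more often retreatment is accepted. A reader who follows the Month 12 to 36 rows as a durability curve would see less loss than has occurred.

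The OLNR repeat goes further, because it selects on a later event. A Category II loss seen at Day 180 is missing from the Day 180 row if that subject is retreated at any later time.

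Time to reduction of response is the study's only secondary objective (section 2.2). Section 6.4 also plans reduction-of-response analyses at the data cutoffs connected with the BLA submission.

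**Working it through.** The SAP states no loss rate, uptake or expected proportion for these endpoints, so there is no figure of its own to reproduce. The check is an illustration for Category II areas.

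**Inputs from the SAP.** There are five visits (Day 180, M12, M18, M24, M36). The denominator rule is that of 7.6.2 and the OLNR definition that of Table 16. Retreatment follows loss. Losses found at M36 are not retreated within the study (Table 3, footnote b).

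**Assumptions, not in the SAP.** A share h of maintained areas loses response in each interval. A share u of new losers is retreated before the next visit. Loss does not reverse and there is no dropout. Every loss qualifies for retreatment.

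**Formulas.** Let s = (1−h)^(k−1) be the share still maintaining response before visit k.

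- Cumulative loss at visit k: 1 − (1−h)^k.
- SAP rule at visit k: [(1−u)(1−s) + h·s] / [s + (1−u)(1−s)]. These are the earlier losers not retreated plus the new losers, over all areas not yet retreated.
- OLNR at visit k: losers by visit k who are never retreated, over all never retreated.

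**Worked values, h = 15%, u = 50%, per 100 areas.**

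- Day 180: 15 lose response and 7.5 of them are then retreated.
- M12: the denominator is 92.5 and new losses are 0.15 × 85 = 12.75. The SAP rule gives (7.5 + 12.75)/92.5 = 21.9%. Cumulative loss is 15 + 12.75 = 27.75, or 27.8%.
- M36: s = 0.85^4 = 0.5220. The SAP rule gives (0.2390 + 0.0783)/(0.5220 + 0.2390) = 41.7%. Cumulative loss is 1 − 0.85^5 = 55.6%.
- OLNR at Day 180: 0.075/0.7610 = 9.9%, against 15.0%.

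**Results for h = 15% (%).**

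| | Day 180 | M12 | M18 | M24 | M36 |
|---|---|---|---|---|---|
| Cumulative loss (also SAP rule at u = 0) | 15.0 | 27.8 | 38.6 | 47.8 | 55.6 |
| SAP rule, u = 50% | 15.0 | 21.9 | 28.7 | 35.3 | 41.7 |
| SAP rule, u = 80% | 15.0 | 17.9 | 21.1 | 24.5 | 28.2 |
| SAP rule, u = 100% | 15.0 | 15.0 | 15.0 | 15.0 | 15.0 |
| OLNR, u = 50% | 9.9 | 18.2 | 25.4 | 31.4 | 41.7 |
| OLNR, u = 80% | 4.9 | 9.0 | 12.5 | 15.5 | 28.2 |

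**Other loss rates at M36, SAP rule against cumulative loss.**

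- h = 5%, u = 50%: 14.7% against 22.6%.
- h = 10%, u = 80%: 18.5% against 41.0%.
- h = 20%, u = 50%: 53.5% against 67.2%.

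**Category I.** If retreatment is unrelated to loss, it removes areas without biasing the proportion. If worse current scores drive it, the proportion is biased downward as in Category II. The SAP does not say which applies.

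**The case against.** A proportion among areas not yet retreated is a legitimate descriptive quantity, and the title of 7.6.2 says that it is prior to retreatment. The tables are descriptive, with no test attached. Several limits on the point stand.

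- **The trigger is narrower than the events counted.** Table 13 asks for no confirmation. A fall from a 3-level to a 2-level improvement is a counted reduction but does not make the area eligible. Unconfirmed losers, subjects excluded from retreatment, decliners and new losers at the visit all remain in the table. A reader might infer that later rows contain only maintained responders and decliners; they do not.
- **The time variable keeps the events.** In the TRR Population Before Retreatment, a subject retreated later still contributes her first loss to the time summary. A reader might infer that every durability output is biased; that summary does not lose these events. It is descriptive only, however, and gives no cumulative proportion by visit, so it does not repair the table.
- **Categories are already shown separately.** Only the Overall column mixes them.
- **The size is assumed.** It is zero at zero uptake. The model gives the double-length M24 to M36 interval the same loss as the others. It also merges the three endpoints into one qualifying loss. Sizes for the separate endpoints would differ, since an area retreated after a lesser loss also leaves the denominator of the graver endpoint.
- **OLNR has a thin mandate.** Table 16 does not list reduction of response for it, and the opening of 7.6 names only the two TRR populations. Section 7.6.2 nevertheless orders the repeat.

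These limits narrow the point. They do not remove the selective exit of Category II losers, and the SAP neither labels the proportions as conditional nor pairs them with a cumulative figure.

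**Conclusion.** The point holds for Category II. From Month 12 on, the 7.6.2 proportions in the TRR Population Before Retreatment fall below cumulative loss whenever some losers are retreated and loss does not reverse. At an assumed 15% loss per interval, the Month 36 shortfall against 55.6% is 13.9 percentage points at 50% uptake (55.6 − 41.7), 27.4 at 80% (55.6 − 28.2), 40.6 at 100% (55.6 − 15.0) and nil at 0%. The SAP does not show where in that range the study will fall.

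The Day 180 proportion in that population is unaffected, because retreatment starts only after the Day 180 assessments. The OLNR repeat is affected at every visit, Day 180 included.

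A reader might go on to infer that durability is overstated for all retreated areas. The document does not support that. Category I areas can be retreated without any loss, so the direction there is unknown, and the Overall column blends a known bias with an unknown one.

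**What to change.** - For each 7.6.2 endpoint, report by category the cumulative incidence of first composite loss by visit. Count an area from its first loss onward whether or not it is later retreated. Treat an area retreated without a prior loss as leaving observation at retreatment, and show the number of such areas.
- Use first loss, rather than fixing only retreated areas as lost while other losers are re-rated at each visit. The two agree only if loss never reverses, and the SAP itself allows for losses that are not confirmed.
- Base the durability conclusion on this summary, by category and not on the Overall column.
- Keep the existing proportions only if they are labelled as conditional on not yet being retreated.
- Do not use OLNR loss-of-response proportions or times as durability estimates. Drop them, or label them as selected on later retreatment. Other OLNR tables can stay.

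The cost is SAP wording and a little more programming on data already collected. No visit or clinical rule changes. The downside is that the durability figures will be less favourable.
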